4.4.4. SF-36 (Both Cohorts)

The 36-item Short Form Health Survey (SF-36) version 2 is a set of generic, coherent, and easily administered QoL measures. It has 36 items grouped in 8 dimensions. For both cohorts, the SF-36 total score, Physical Component Summary (PCS), Mental Component Summary (MCS), and domain scores as defined in Table 7 will be summarized by treatment group at baseline and each post-baseline time point using descriptive statistics for continuous variables for the observed value as well as the change from baseline.

The longitudinal changes in SF-36 will be analyzed using MMRM method specified in Section 4.3.1.1 except the log-transformation of SF-36 is not performed. Change from baseline in SF-36 at Weeks 26 and 50 will be summarized for each treatment group from the MMRM analysis and no formal treatment comparison will be made. The point estimate and 2-sided 95% CI for the change from baseline of SF-36 will be presented. Data collected on or after receipt of additional standard of care therapy (LN cohort only) or treatment discontinuation will be assumed missing and handled in the MMRM model as MAR.

Refer to Section 6.3 for a more detailed description of the SF-36 calculation and scoring methods.

Table 7: SF-36 Domain Scores

Scale	Number of Items	Definition of Scale
Physical Functioning (PF)	10	Limitations in physical activity because of health problems
Social Functioning (SF)	2	Limitations in social activities because of physical or emotional problems
Role Limitations Due to Physical Health (RP)	4	Limitations in usual role activities because of physical health problem
Bodily Pain (BP)	2	Prescence of pain and limitations due to pain
General Health (GH)	5	Self-evaluation of personal health
Mental Health (MH)	5	Psychological distress and well-being
Role Limitations Due to Emotional Problems (RE)	3	Limitations in usual role activities because of emotional problems
Vitality (VT)	4	Energy and fatigue

Abbreviation: SF-36 = 36-item Short Form Health Survey

4.4.5. EQ-5D-5L (Both Cohorts)

The 5-level EuroQol-5 Dimensions (EQ-5D-5L) is a self-reported standardized instrument to measure health-related QoL and has been used in a wide range of health conditions. The EQ-5D-5L is defined by 5 dimensions: mobility, usual activities, self-care, pain/discomfort, and anxiety/depression. A 0 to 1 health state index score (or utility score), where 0 indicates a health state equivalent to death and 1 indicates perfect health, will be calculated from individual health profiles using a US TTO value set. Negative values indicate health states considered worse than death.

Refer to Section 6.3 for a more detailed description of the EQ-5D-5L calculation and scoring methods.

For both cohorts, the EQ-5D-5L index score and visual analog scale (VAS) score will be summarized by treatment group at baseline and each post-Baseline time point using descriptive statistics for continuous variables for the observed value as well as the change from baseline.

Change from baseline in EQ-5D-5L scores at Weeks 26 and 50 will also be analyzed using the same MMRM method, and no formal treatment comparison will be made. The point estimate and 2-sided 95% CI for the change from baseline of EQ-5D-5L scores will be presented. Data collected on or after receipt of additional standard of care therapy or treatment discontinuation will be assumed missing and handled in the MMRM model as MAR.

4.4.6. Exploratory Biomarkers (Both Cohorts)

Exploratory blood and urine biomarker analyses will be documented in a separate biomarker SAP.

4.4.7. Time to First CRR or PRR (LN Cohort Only)

For LN cohorts, time to the first occurrence of CRR or PRR will be summarized by spot urine sample.

Participants will be censored at the earliest of their treatment discontinuation time, receipt of additional standard of care therapy, study withdrawal or death, or at Week 50 when the event of CRR or PRR has not yet occurred.

The analysis will be performed using 2 approaches:

- Time to the first CRR (using spot UPCR)
- Time to the first CRR or PRR (using spot UPCR) time to the first event (either CRR or PRR, whichever occurred first)

Kaplan-Meier will be used for estimating the survival curve. The corresponding Kaplan-Meier curve for each treatment group will be created by plotting the cumulative proportion surviving against the survival times.

The curves for the ALXN2050 180 mg and placebo treatment groups will be statistically compared with a log-rank test of the null hypothesis that there is no difference between the population survival curve over time. A corresponding summary table will present the CDF estimate, the number of participants at risk, the number of participants responding (ie, occurrence of first CRR or PRR), and the number of participants censored at each post-Baseline time point by treatment group. The table will also present first quartile, median, and third quartile, along with corresponding 2-sided 95% CI of time to response.

4.4.8. Overall Renal Response (LN Cohort Only)

For the LN cohort, Overall Renal Response (ORR) is defined as the composite of CRR and PRR.

The percentage of participants meeting the criteria for ORR will be summarized at Weeks 26 and 50 by treatment group by calculating the point estimate and 2-sided 95% CI based on exact confidence limits using the Clopper-Pearson method.

Participants with additional standard of care therapy (LN cohort only) or treatment discontinuation will be treated as failure to meet ORR criteria and considered nonresponders.

4.4.9. Time to the First Occurrence of UPCR > 50% Decrease from Baseline (LN Cohort Only)

For the LN cohort, time to the first occurrence of UPCR > 50% decrease from baseline will be summarized by spot urine sample.

Participants will be censored at the earliest of their treatment discontinuation time, receipt of additional standard of care therapy, study withdrawal or death, or at Week 50 when the event of UPCR > 50% decrease has not yet occurred.

Kaplan-Meier will be used to estimate the survival curve. The corresponding Kaplan-Meier curve for each treatment group will be created by plotting the cumulative proportion surviving against the survival times.

The curves for the ALXN2050 180 mg and placebo treatment groups will be statistically compared with a log-rank test of the null hypothesis that there is no difference between the population survival curve over time. A corresponding summary table will present the CDF estimate, the number of participants at risk, the number of participants responding (ie, occurrence of UPCR decrease > 50%), and the number of participants censored at each post-Baseline time point by treatment group. The table will also present first quartile, median, and third quartile, along with corresponding 2-sided 95% CI of time to response.

4.4.10. FACIT-Fatigue Total Score (LN Cohort Only)

For the LN cohort, the Functional Assessment of Chronic Illness Therapy (FACIT-Fatigue total score will be summarized by treatment group at baseline and at Weeks 26 and 50 for the change from baseline using descriptive statistics for continuous variables.

The longitudinal changes in FACIT-Fatigue total score will be analyzed using MMRM method specified in Section 4.3.1.1, except the log-transformation of score is not performed.

Change from baseline at Weeks 26 and 50 will be summarized for each treatment group from the MMRM analysis, and no formal treatment comparison will be made. The point estimate and

2-sided 95% CI for the change from baseline of FACIT-Fatigue total score will be presented. Data collected on or after receipt of additional standard of care therapy or treatment discontinuation will be assumed missing and handled in the MMRM model as MAR.

Refer to Section Error! Reference source not found. for a more detailed description of the FACIT-Fatigue calculation and scoring methods.

4.4.11. Histology (LN Cohort Only)

For participants in the LN cohort who complete an optional post-treatment biopsy at Week 50, changes in histology will be summarized using the central pathology biopsy results. Activity index and chronicity index scores will be summarized at baseline and at Week 50 by treatment group using descriptive statistics for the observed value as well as the change from baseline. In addition, shift tables will display the change in LN class, C3 staining, and C1q staining from pretreatment renal biopsy to post-treatment renal biopsy.

4.4.12. Anti-dsDNA and Anti-C1q Antibodies (LN Cohort Only)

For the LN cohort, anti-dsDNA and anti-C1q antibodies will be summarized at baseline and at Weeks 26 and 50 by treatment group using descriptive statistics for the observed value as well as the change from baseline.

In addition, the proportion of participants with anti-dsDNA antibodies below the lower limit of normal (LLN) and with anti-C1q antibodies below the LLN will be summarized descriptively at each study visit by treatment group by calculating the point estimate and 2-sided 95% CI, based on exact confidence limits using the Clopper-Pearson method.

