2.2.3. Rationale for Evaluating ALXN2050 in Participants with Lupus Nephritis

Lupus nephritis occurs in approximately 50% of patients with SLE (Almaani, 2019; Morales, 2021), an autoimmune disorder caused by loss of tolerance to self-antigens, the production of autoantibodies, and deposition of complement-fixing ICs in injured tissues (Bao, 2015). The diagnosis of LN is determined by kidney biopsy according to the 2018 International Society of Nephrology/Renal Pathology Society (ISN/RPS) nomenclature and

classification revised from the 2003 report (Bajema, 2018; Markowitz, 2007). In total, there are 6 classes of LN: Classes I to VI (Markowitz, 2007). The subset of patients with SLE that develop LN have the worst prognosis. Lupus nephritis leading to CKD is an independent major risk factor for overall mortality and morbidity attributed to cardiovascular diseases (Gasparotto, 2020). With current induction and maintenance therapies, the 5-year mortality is approximately 20%, and the risk of developing ESRD at 5, 10, and 15 years is 11%, 17%, and 22%, respectively

(Tektonidou, 2016). Recurrence of LN after treatment (Renal Flare) occurs within 1 year in up to 25% of patients and is associated with increased risk of CKD progression (Almaani, 2017).

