8.1.7. Extrarenal Systemic Lupus Erythematosus Flare (LN Cohort Only)

The Systemic Lupus Erythematosus Disease Activity Index 2000 (SLEDAI-2K) is an instrument that assesses the disease activity of SLE. This instrument will be used for the monitoring of Extrarenal SLE Flare in the LN Cohort.

Extrarenal SLE Flare is defined as an increase in SLEDAI-2K Safety of Estrogens in Lupus Erythematosus National Assessment (SELENA) Modification ≥ 4 points (see Section 8.11.2) that is not accounted for by proteinuria, hematuria, urinary cellular casts, hypocomplementemia, or an increase in anti-double-stranded DNA (anti-dsDNA) antibody level.

Participants in the LN cohort who meet the criteria for Extrarenal SLE Flare may receive additional standard of care therapy, if considered clinically appropriate by the Investigator. If additional standard of care therapy is administered, the event is considered a severe Extrarenal SLE Flare.

Participants will be allowed to receive a limited number of corticosteroid treatments for non-severe Extrarenal SLE Flare, if clinically warranted as outlined below. Such treatment will not be considered additional standard of care therapy and affected participants will not be considered Treatment Failure.

- Up to 2 corticosteroid treatments will be allowed for a non-severe Extrarenal SLE Flare.
- One corticosteroid treatment will be allowed between Week 12 (end of steroid taper) and Week 22 (4 weeks prior to the Week 26 primary endpoint).
- One corticosteroid treatment will be allowed between Week 26 and Week 46 (4 weeks prior to the Week 50 analysis).
- Each treatment course should be no longer than 14 days in duration with the steroid dose returning to 7.5 mg/day by Day 14.
- Up to a total of 20 mg/day (prednisone or prednisone equivalent) is permitted.
- There can be no concurrent worsening of renal disease (as defined by the criteria for a Renal Flare).

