8.11.2. SLEDAI–2K (LN Cohort Only)

The SLEDAI–2K tool assesses disease activity across 24 disease descriptors. The total score ranges from 0 to 105, with higher scores representing more significant degrees of disease activity and covers a recall period of ≤ 30 days. The SLEDAI–2K assessment will be used for the determination of Extrarenal SLE Flare (Section 8.1.7). For the purpose of assessment for presence of Extrarenal SLE Flare, the following 6 descriptors will not be accounted for: proteinuria, hematuria, urinary casts, hypocomplementemia, pyuria, and increase in the anti-dsDNA antibody level. As a result, the total number of disease activity descriptors assessed is 18 and the total score ranges from 0 to 85.

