- Baseline FACIT-Fatigue score: descriptive statistics (n, mean, median, SD, minimum, maximum)
- Baseline anti-dsDNA autoantibodies: descriptive statistics (n, mean, median, SD, minimum, maximum) and frequency of participants with antibody levels < LLN
- Baseline anti-C1q autoantibodies: descriptive statistics (n, mean, median, SD, minimum, maximum) and frequency of participants with antibody levels < LLN
- Concomitant therapy with SGLT-2 inhibitors (Yes, No)

For the IgAN cohort, the following additional disease characteristics will be summarized:

- Baseline 24-hour urine protein (g/day): descriptive statistics (n, mean, median, SD, minimum, maximum) and frequency of participants in the following categories:
 (1-2 g/day, > 2 g/day)
- Baseline 24-hour UPCR (g/g): descriptive statistics (n, mean, median, SD, minimum, maximum)
- Time from eligibility biopsy to randomization (< 1 month, 1-3 months, 3-6 months, 6-12 months, 12-24 months, > 24 months)
- MEST-C score based on central pathology (M0, M1, E0, E1, S0, S1, T0, T1, T2, C0, C1, C2)
- C3 staining based on central pathology (0+, 1+, 2+, 3+)
- Clq staining based on central pathology (0+, 1+, 2+, 3+)
- Concomitant therapy with SGLT-2 inhibitors (Yes, No)

The agreement between local and central pathology diagnosis will be assessed for each disease cohort by inter-rater reliability analysis using the kappa statistic reported with Cohen's K-coefficient and its 95% CIs. In addition, if central pathology results are limited, then local pathology results may be summarized as well in the disease characteristic summary.

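### The added anti-dsDNA and anti-C1q proportion counts values below the LLN, so it does not capture normalisation or separate raised from normal participants at baseline

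*SAP*

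**What the plan says.** SAP 4.4.12 has two parts. The first summarises anti-dsDNA and anti-C1q as observed values and change from baseline, at baseline and Weeks 26 and 50. This matches the exploratory endpoint in protocol Section 3, Table 7. The second part adds "the proportion of participants with anti-dsDNA antibodies below the lower limit of normal (LLN) and with anti-C1q antibodies below the LLN", by treatment group, with exact 95% confidence intervals.

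SAP 6.2.2.2 repeats the limit among the LN baseline characteristics, once for each antibody: "Baseline anti-dsDNA autoantibodies: descriptive statistics (n, mean, median, SD, minimum, maximum) and frequency of participants with antibody levels < LLN" and "Baseline anti-C1q autoantibodies: descriptive statistics (n, mean, median, SD, minimum, maximum) and frequency of participants with antibody levels < LLN".

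On direction, protocol 8.11.2 lists the SLEDAI-2K activity descriptors that are set aside when an extrarenal flare is assessed. They include "hypocomplementemia, pyuria, and increase in the anti-dsDNA antibody level". Protocol 8.1.7 defines that flare as a score increase not explained by several items, among them "or an increase in anti-double-stranded DNA (anti-dsDNA) antibody level". Protocol 2.2.3 describes SLE as "an autoimmune disorder caused by loss of tolerance to self-antigens, the production of autoantibodies" and deposition of immune complexes.

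**The concern.** Low values are the abnormal ones for complement. Protocol 2.2.3 links falls in C3, C4 and C1q to LN and its flares, and SAP 6.2.2.2 accordingly counts participants with low C3 and low C4. For an autoantibody whose rise marks activity, the favourable change is from raised to normal, and the limit that separates those two states is the upper one. A count below the lower limit answers a different question.

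Two things are at stake. At baseline, the reader cannot see how many participants in each arm had raised antibodies. After baseline, a low or zero proportion in every arm could be misread as no effect on autoantibodies when it only reflects the limit chosen.

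**Working it through.** The plan gives no figure to reproduce here, so the check is mainly of the text.

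**Which limit is meant.** SAP 4.4.12 spells LLN out as the lower limit of normal, and the SAP abbreviation list does the same. The SAP also defines the ULN and uses it for liver enzymes in 4.5.3.1. < LLN is applied to both antibodies in two sections, so it is not an isolated slip. Neither section gives an alternative ULN-based or positive/negative count.

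**What each rule counts.**

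| Antibody value | Counted by < LLN | Counted by ≤ ULN |
|---|---|---|
| Above ULN (raised) | No | No |
| LLN to ULN (normal range) | No | Yes |
| Below LLN | Yes | Yes |

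Under the planned rule the first two rows are indistinguishable. Those are the rows that matter both for baseline status and for a move from raised to normal.

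**Size, under stated assumptions.** The documents give no assay reference ranges, so two cases are shown for an arm of 30 (protocol Table 8: 30 on 180 mg, 10 on 120 mg, 30 on placebo).

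- *Case A: LLN is zero or undefined.* Nobody can fall below it. The result is 0/30. The exact upper limit is 1 − 0.025^(1/30) = 0.116, so 0% (95% CI 0% to 11.6%), whatever the true rate.
- *Case B: LLN is the 2.5th percentile of a two-sided 95% reference interval.* Suppose every participant in the arm has normalised and the values are distributed as in healthy people. The expected count below the LLN is 30 × 0.025 = 0.75, and the chance of seeing none is 0.975^30 = 0.47. The expected count at or below the ULN in the same arm is 30 × 0.975 = 29.25.

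**What the corrected rule would show.** For an assumed 20% to 50% at or below the ULN, with n = 30 and Clopper-Pearson limits:

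| Count | Proportion | 95% CI |
|---|---|---|
| 6/30 | 20% | 7.7% to 38.6% |
| 9/30 | 30% | 14.7% to 49.4% |
| 12/30 | 40% | 22.7% to 59.4% |
| 15/30 | 50% | 31.3% to 68.7% |

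In Case A the planned rule reports 0/30 on every one of these lines.

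**The case against.** The strongest reply is that the endpoint does not depend on this proportion. Observed values and change from baseline are planned and are exactly what the protocol lists. That stands. A reader might infer that normalisation is never measured, or that the plan cannot show an effect on autoantibodies. The documents do not support either reading, because the continuous summaries can show a fall. In addition, SAP 4.5.3.1 plans normal/low/high shift tables and listings of all laboratory data. The shift paragraph names chemistry, hematology, coagulation and urinalysis, so coverage of autoantibodies is neither stated nor excluded. A separate biomarker plan (SAP 4.4.6) might also touch them, although protocol Table 13 lists autoantibodies outside its exploratory-biomarker row.

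Second, LLN may be loose wording for the assay's negativity cut-off, in which case the proportion would work as a seronegativity rate. The documents do not rule that out. But the term is written out as the lower limit of normal, and a programmer following the text would apply that limit.

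Third, the protocol passages on direction concern anti-dsDNA only. This stands too: for anti-C1q the direction is an inference from its being a disease autoantibody summarised alongside anti-dsDNA.

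Fourth, no endpoint in either document is seroconversion or normalisation, so a responder rate among participants raised at baseline would be a new analysis. That is fair, and it is why that part of the remedy is optional.

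**Conclusion.** The point holds for the categorical summary only. As written, the proportion in SAP 4.4.12 and the baseline frequencies in SAP 6.2.2.2 neither capture normalisation nor separate raised from normal participants. For anti-dsDNA this follows from the protocol's own treatment of a rise as activity; for anti-C1q it rests on the inference above. It also assumes that LLN means what the SAP says it means.

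A reader might go further and expect 0% in every arm at every visit. That is Case A only, and the reference ranges that would settle it are not in the documents.

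The consequence is minor. The summary is exploratory and descriptive, concerns the LN cohort alone, and has no bearing on the primary or secondary endpoints or on power. The values themselves are kept, so a correct proportion can be derived at any time.

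**What to change.** In SAP 4.4.12 and in both antibody bullets of SAP 6.2.2.2, replace < LLN with at or below the ULN (or the assay's negativity cut-off), and state the limit used for each assay. If the negativity cut-off was intended all along, naming it resolves the point. Optionally, also report the post-baseline proportion among participants who were above that limit at baseline, with the denominator shown.

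The cost is wording in two SAP sections and the matching table specifications. No new sampling is needed: protocol Tables 1 and 3 already schedule autoantibody samples at Screening, Day 1, Week 26 and Week 50.

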4.4.13. Slope of eGFR (IgAN Cohort Only)

For the IgAN cohort, slope of eGFR will be computed using a linear mixed-effect model including data through Week 26 or 50, respectively. The model will include eGFR as the response variable, random participant effects for intercepts and slopes, fixed categorical effects of treatment group and randomization stratification factor, treatment group by visit interaction, and a fixed, continuous effect of visit.

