	Change from baseline in eGFR at Weeks 102 and 154		
To evaluate the efficacy of ALXN2050 on hematuria in participants with LN or IgAN	Absolute value and change from baseline in RBC in urine from baseline to Weeks 26 and 50		
	Achieving < 10 RBC/hpf		
To assess quality of life based on participant- reported outcomes in participants with LN or	Change from baseline in SF-36v2 at Weeks 26 and 50		
IgAN based on treatment with ALXN2050	Change from baseline in EQ-5D-5L at Weeks 26 and 50		
To evaluate biomarkers such as complement, autoimmune, and renal in participants with LN or IgAN	Absolute values and change from baseline in levels of biomarkers in blood and urine over time		
Exploratory (LN Cohort Only)			
To assess the efficacy of ALXN2050 in	Time to the first CRR or PRR (using spot UPCR)		
exploratory efficacy endpoints	Meeting the criteria for overall renal response (CRR or PRR) at Weeks 26 and 50		
	Time to the first occurrence of UPCR > 50% decrease from baseline (using spot UPCR)		
To assess quality of life based on participant- reported outcomes	Change from baseline in FACIT-Fatigue total score at Weeks 26 and 50		
To assess the efficacy of ALXN2050 in other exploratory endpoints	Histology changes from baseline to Week 50, if tissue is available		
	Absolute values and change from baseline in anti-dsDNA and anti-C1q antibodies at Weeks 26 and 50		
Exploratory (IgAN Cohort Only)			
To assess the efficacy of ALXN2050 in exploratory efficacy endpoints	Slope of eGFR computed from baseline to Weeks 26 and 50		
	•		

Abbreviations: anti-C1q = anti-C1q complement component; anti-dsDNA = anti double-stranded DNA; AP = alternative pathway; Bb = Bb fragment of complement factor B; CRR = complete renal response; eGFR = estimated glomerular filtration rate; EQ-5D-5L = 5-level EuroQol-5 Dimensions; FACIT-Fatigue = Functional Assessment of Chronic Illness Therapy – Fatigue Scale; IgAN = immunoglobulin A nephropathy; LN = lupus nephritis; PD = pharmacodynamic; PK = pharmacokinetic(s); PRR = partial renal

Table 1: Objectives and Endpoints

Objectives	Endpoints

response; RBC = red blood cells; SF-36v2 = 36-item Short Form Health Survey version 2; SLE = systemic lupus erythematosus; TEAE = treatment-emergent adverse event; TESAE = treatment-emergent serious adverse event; UPCR = urine protein-to-creatinine ratio

Primary Estimand

The estimand is described by the following attributes:

- Population: Full Analysis Set (FAS)

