4.1.2. Data Presentation for the 24-Week Blinded Extension Treatment Period

For the LN cohort, data summaries for the 24-week Blinded Extension Treatment Period will be presented by randomized treatment group and total when applicable.

For the IgAN cohort, summaries will be presented by treatment sequence (ie, "ALXN2050 180 mg", "ALXN2050 120 mg" and "Placebo to ALXN2050 180 mg" or "Placebo to ALXN2050 120 mg"). ALXN2050 Total, which consists of all the participants who were treated with ALXN2050 during the 24-week Blinded Extended Treatment Period, will be added when applicable. "ALXN2050 120 mg & 180 mg" which consists of participants who initially randomized to ALXN2050, will be included in efficacy tables when applicable. In addition, the baseline for the IgAN cohort will be defined as the originally randomized baseline and re-baseline will be defined as the last measurement collected prior to Week 26.

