4.3.1. Secondary Endpoints

4.3.1.1. Percentage Change in Proteinuria from Baseline to Week 50 (Both Cohorts)

The percentage change from baseline in proteinuria at Week 50 will be analyzed using a mixed-effect model for repeated-measures (MMRM) using all available data up to Week 50 (either complete or partial). The data after the intercurrent events will be treated as missing. The model will include change from baseline in log-transformed proteinuria as the response variable and fixed, categorical effects of treatment sequence group, randomization stratification factor, visit, and treatment sequence group by visit interaction as well as a fixed, continuous effect of baseline log proteinuria as a covariate. An unstructured covariance matrix will be used to model the correlations among repeated measurements within each participant. If this analysis fails to

converge, a first-order autoregressive covariance matrix will be used. The Kenward-Roger approximation will be used to estimate denominator degrees of freedom.

For the LN cohort, the treatment effect will be evaluated for the ALXN2050 180 mg bid and placebo treatment groups using a contrast for treatment group-by-visit term at Week 50. The point estimate and 2-sided 90% CI for the mean difference of log-transformed proteinuria will be back-transformed (via exponentiation) to obtain the GMR and corresponding 2-sided 90% CI. The values will then be expressed as percentage change in adjusted geometric mean of proteinuria at Week 50 relative to baseline. The treatment effect will be evaluated for the ALXN2050 120 mg & 180 mg bid and placebo treatment group in the same model mentioned above.

For the IgAN cohort, participants initially randomized to the placebo treatment group will switch to receive either ALXN2050 180 mg bid or ALXN2050 120 mg bid at Week 26. Percentage change from baseline in proteinuria at Week 50 will be summarized for each treatment sequence group from the MMRM analysis and no formal treatment comparison will be made. In addition, percentage change from re-baseline (ie, Week 26) in proteinuria at Week 50 will also be summarized for each treatment sequence group descriptively.

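### IgAN eGFR slope through Week 50: a single line per group runs across the Week 26 placebo-to-ALXN2050 switch, so the placebo-origin slope mixes two treatments

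*SAP*

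**What the plan says.** SAP Table 1 lists the exploratory IgAN endpoint as "Slope of eGFR computed from baseline to Weeks 26 and 50"; Protocol Table 7 defines it in the same way. SAP 4.4.13 implements it with two fits: "slope of eGFR will be computed using a linear mixed-effect model including data through Week 26 or 50, respectively". The model has random participant intercepts and slopes, "fixed categorical effects of treatment group and randomization stratification factor", and "treatment group by visit interaction, and a fixed, continuous effect of visit". It contains no knot, period term, time-varying treatment or cut at the switch.

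SAP 4.3.1.1 states that IgAN participants randomized to placebo "will switch to receive either ALXN2050 180 mg bid or ALXN2050 120 mg bid at Week 26". Protocol 4.1.2 makes that assignment 1:1 at randomization.

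Other sections take account of the switch. SAP 4.1.2 has the rule "For the IgAN cohort, summaries will be presented by treatment sequence" for the extended period. SAP 4.3.1.1 and 4.3.1.3 add a Week 26 re-baseline for the IgAN cohort and make no formal comparison, and 4.4.2 reports by treatment sequence group. Section 4.4.13 refers only to treatment group and does not use the re-baseline. SAP 4.1.2 also keeps the starting point: "the baseline for the IgAN cohort will be defined as the originally randomized baseline".

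**The concern.** A straight line cannot bend at Week 26. If ALXN2050 alters the course of eGFR, the placebo-origin line through Week 50 is an average over two treatments and estimates neither the placebo slope nor the drug slope. The MMRM analyses do not share this problem, because their categorical visit effect gives each visit its own mean.

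SAP 4.7 includes all planned efficacy analyses in the Week 50 reporting. A slope reported there for the placebo group would naturally be set beside the 180 mg slope, and the gap between them would not be an estimate of drug against placebo over 50 weeks. What is at stake is the reading of one exploratory endpoint. The primary and secondary endpoints are not involved.

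**Working it through.** The documents state no effect size, power or variance for the eGFR slope, so there is no planned figure to reproduce. The check is how much of a true slope difference survives the single-line fit.

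**Inputs**
- IgAN eGFR visits (Protocol Tables 2 and 4): Day 1 (taken as week 0) and Weeks 2, 6, 12, 18, 26, 28, 32, 38, 42 and 50. There is also a Screening value up to 6 weeks earlier; SAP 4.4.13 does not say whether it enters the model.
- Switch at Week 26, with Week 26 assessments before dosing (SAP 4.1.1).
- Assumption, for illustration only: slopes of -6 on placebo and -3 on drug, in mL/min/1.73 m² per year.

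**Formula.** With complete visits and random intercepts and slopes, the mixed-model group slope equals the least-squares slope. Let b_p and b_a be the placebo and drug slopes. The placebo-origin mean is b_p·min(t,26) + b_a·[t − min(t,26)]. Let f be the least-squares slope of min(t,26) on t. Then:
- fitted placebo-origin slope = f·b_p + (1 − f)·b_a
- fitted difference = f·(b_a − b_p)

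So f is the fraction of the true difference that is kept, whatever the slopes are.

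**Numbers.** For the 11 visits, with m = min(t,26): Σt = 254, Σt² = 8700, Σm = 194, Σtm = 6124.

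f = (6124 − 254·194/11) / (8700 − 254²/11) = 1644.36 / 2834.91 = 0.580

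| Case | Fraction kept | Shrinkage |
|---|---|---|
| Day 1 to Week 50 | 0.580 | 42% |
| plus Screening at week −4 | 0.622 | 38% |
| plus Screening at week −6 | 0.630 | 37% |
| Through Week 26 only | 1.000 | none |

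In the example, the fitted placebo-origin slope is 0.580·(−6) + 0.420·(−3) = −4.74, and the fitted difference is 1.74 instead of 3.00.

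A small simulation of the mixed model on the Day 1 to Week 50 visits (60 runs, 24 per arm, same slopes) gave a mean difference of 2.04 with standard error 0.19. That is clearly below 3.00 and within sampling error of 1.74.

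**Departures from the simple case** (Day 1 to Week 50 visits)
- Delayed onset of 4, 8 or 12 weeks: the difference is 0.67, 0.74 or 0.82 of what the same line would show without a switch, so the shrinkage is 33%, 26% or 18%.
- Weaker 120 mg effect: if 120 mg had half the slope effect of 180 mg (assumption), the average effect after the switch is 0.75 of the 180 mg effect. Against 180 mg the shrinkage is about 0.42·0.75 = 31%.
- Acute step of s mL/min/1.73 m² at drug start. Regressing the indicator of t > 0 on t gives (254 − 10·254/11)/2834.91·52 = 0.424 per year. For t > 26 it gives (190 − 5·254/11)/2834.91·52 = 1.367 per year. The difference through Week 50 is then 3.00 + 0.424·s without the switch and 1.74 + (0.424 − 1.367)·s with it.

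| Step s | Week 50 difference, no switch | Week 50 difference, with switch |
|---|---|---|
| −2 | 2.15 | 3.63 |
| 0 | 3.00 | 1.74 |
| +2 | 3.85 | −0.15 |

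The bias from the switch can therefore inflate the difference, shrink it or reverse its sign.

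**With a knot.** Since min(t,26) = t − max(t − 26, 0), adding max(t − 26, 0) for the switching participants represents the broken line exactly. Under a pure slope effect the pre-switch slope, and so the full 3.00, is recovered.

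**The case against.** Four points on the other side carry weight.

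1. No comparison is planned. SAP 4.4.13 names slopes but no test or contrast, SAP 4.4 makes the exploratory analyses descriptive, and the neighbouring IgAN Week 50 analyses rule out formal comparison. This stands: the contrast is one that a reader would form.
2. The sequence rule in SAP 4.1.2 may govern the display, and the SAP uses treatment group loosely elsewhere. This stands as far as labelling goes. Splitting placebo by sequence gives two lines, each still straight through the switch.
3. The unmixed randomized slope is already planned, as the through-Week-26 fit. This stands and limits the damage.
4. The protocol itself defines a baseline-to-Week-50 slope, so the SAP carries out the stated endpoint. This also stands. It argues for keeping that slope under a correct label and adding segment slopes beside it.

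A reader might go further and infer that the Week 50 analysis understates the drug effect by a fixed 42%. The documents do not support that. They give no slopes, and 42% is the top of the pure slope-effect cases calculated: it needs immediate onset, equal dose effects and no Screening value in the model. With an acute step even the direction is not assured.

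**Conclusion.** The point holds as a matter of model structure. As written, the Week 50 fit gives a placebo-origin slope covering about 26 weeks of placebo and 24 weeks of ALXN2050, and any comparison of it with the ALXN2050 slopes is biased. Under a pure slope effect with immediate onset and equal dose effects, the difference from placebo shrinks by about 37-42%; the delayed-onset and weaker-dose cases above give 18-33%. With an acute eGFR step the bias can go either way. All figures assume complete visits.

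The switch affects neither the through-Week-26 slopes nor the slopes of the groups randomized to ALXN2050. An acute step would pull the Week 26 difference away from the long-term one too (0.79 for s = −2 and 5.21 for s = +2, against 3.00), but that is a separate matter of total against chronic slope. It would be wrong to infer that the eGFR slope evidence as a whole is unusable. This is a minor, inexpensive correction to a descriptive exploratory analysis.

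**What to change.** In the through-Week-50 model of SAP 4.4.13:
- Add a knot at Week 26 for the participants who switch from placebo. Use one common placebo slope before Week 26, when their treatment is identical, and post-switch slopes by sequence, pooled over dose if the data are too sparse. Label them by sequence as in SAP 4.1.2.
- Base any comparison with placebo on the Week 0-26 slope only.
- If the single baseline-to-Week-50 slope is kept because the protocol names it, label it for placebo-origin participants as a switch-sequence slope, not a placebo slope.
- State whether the Screening eGFR enters the model, and record the added segment slopes in SAP 4.8.

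The cost is a short SAP edit and less precise segment slopes: about 12 participants per switch sequence (24 placebo participants split 1:1), followed for 24 weeks after the switch. A knot does not model an acute step. If one is thought plausible, it needs its own term or a stated caveat.
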